Exclusion Criteria:

- Under 18 years old
- Does not speak English
- Unable to consent to involvement in the research study

- Is pregnant
- Has a bleeding disorder/diagnosis
- Currently taking anticoagulant medications and not stopped for procedure
- Documented low platelets (<100,000)
- Had a biopsy taken immediately prior to the endobronchial ultrasound

Sample Size Determination: A power analysis was conducted using a small to medium effect size (0.3), power of 0.8, and level of significance 0.05. It was determined that 44 patients would be needed in each group, for a total sample size of 88 patients. To allow for the possibility of removing participants from the final analysis due to missing data, we plan to enroll 120 patients (60 in each group).

- **Data Collection**

Before the study begins, information about the study will be provided to the providers and endoscopy team members, including information about the study purpose, inclusion/exclusion criteria, and procedures.

When a patient who meets the inclusion/exclusion criteria arrives for an appointment, a nurse from the study team will describe the study, answer any questions the patient has, and if the patient wants to enroll in the study, the study team nurse will review the information consent form. After the patient provides written informed consent, the nurse will remove the next envelope out of a box of prefilled and sealed opaque envelopes. The envelope will provide the Subject ID number to be used on all study-related documentation and the study Arm that the patient has been randomized to, either:

1. Cold saline group
2. Standard care group

These envelopes will be filled using a computerized simple random number generator (1:1 randomization) prior to the start of the study.

In addition to the group assignment, the envelope will include a data collection form. Data will be recorded directly on this form during the patient's visit. The form will collect the following information:

- Whether patient was assigned to the cold saline group or the standard care group
- Patient demographics including age, gender, current anticoagulant medications, current cancer diagnoses
- Temperature of cold saline (cold saline group only)
- Time cold saline placed (cold saline group only)
- Volume of cold saline used for irrigation
- Time each biopsy was obtained
- Number of biopsies
- Gauge of needle used to perform biopsy
- Type of suction used (i.e. slow-pull or 5mL, 10mL)

- Number of slides prepared

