- Number of slides that were successfully read
- Number of slides unable to be read due to blood on slide
- Whether another biopsy was attempted
- Whether the procedure was stopped without successful slide reading
- Whether patient needed epinephrine post-biopsy to stop bleeding
- Name of MD performing biopsy
- Start and end time of procedure

After the procedure, the RN will complete the data collection form and place the signed informed consent form and data collection form in the locked resource nurse's office in an area designated for study materials.

On the data collection forms, RNs are instructed to call a member of the study team immediately if there are any safety concerns related to the cold saline. If the study team receives a call about a safety concern, recruitment and enrollment of new participants will stop until the study team meets and reviews the incident with the pulmonologist involved and determines it is safe to continue. The study team includes nurses with clinical experience and expertise in endobronchial biopsy procedures. They will consult with the medical team if any adverse events arise. Any adverse events and serious adverse events will be reported to the IRB in compliance with IRB safety policies.

- **Intervention or experimental aspect of the study**

In patients randomized to Arm 1, the clinician will scan the cold saline using the infrared temperature scanner and confirm saline is between 33-39 degrees Fahrenheit. Then after identifying the lymph node or lesion to be biopsied on ultrasound, using the endobronchial ultrasound scope, two 60mL syringes of cold saline will be inserted, through the biopsy channel of the endobronchial ultrasound scope, directly onto the bronchial wall where the biopsies are to be performed. The saline will then be sucked out of the airway using the endobronchial ultrasound scope. The FNA needle or biopsy forceps will then be passed down the biopsy channel of the endobronchial ultrasound scope, and the biopsy will be obtained. Cold saline irrigation is part of the normal procedure and may cause coughing. The study may benefit these patients if the preventive cold saline irrigation prevents bleeding.

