Patients randomized to Arm 2 will receive standard care that includes no irrigation with cold saline prior to the biopsy. After identifying the lymph node or lesion to be biopsied on ultrasound, the FNA needle or biopsy forceps will then be passed down the biopsy channel of the endobronchial ultrasound scope, and the biopsy will be obtained.

In both Arm 1 and Arm 2, TriHealth pulmonologists will conduct the endobronchial ultrasound and biopsy according to standard clinical practice. Patients will receive the same care procedure and biopsy that they would receive if they were not enrolled in the study. The only research procedure is that patients in Arm 1 will receive irrigation of the biopsy site with cold saline before the biopsy is performed. The rest of the procedure will follow standard clinical practice.

Data recorded on paper data collection forms will be entered into a password protected database. Only study team members will have access to the database. No personal information will be entered into the electronic database. Data will undergo range checks when entered in the database, and quality control procedures will be performed to ensure accuracy of the data in the electronic database.

- **Statistical Analysis**

Statistical analyses will be performed using Intellectus Statistics statistical software. The following analyses will be performed to address each hypothesis:

- Hypothesis 1: Patients undergoing endobronchial ultrasound and biopsy who receive irrigation with cold saline prior to biopsy will experience a lower incidence of unreadable biopsy slides compared to patients undergoing endobronchial ultrasound and biopsy who do not receive irrigation with cold saline prior to biopsy.

To compare the effects of the intervention, a Chi Square test will be used to compare frequency of unreadable biopsy slides among patients who received the cold saline irrigation compared to patients who did not receive the cold saline irrigation. A level of significance of $\alpha=0.05$ will be used.

- Hypothesis 2: Patients undergoing endobronchial ultrasound and biopsy who receive irrigation with cold saline prior to biopsy will experience a lower incidence of having to reperform biopsies in order to obtain readable slides compared to patients undergoing endobronchial ultrasound and biopsy who do not receive irrigation with cold saline prior to biopsy.

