To compare the effects of the intervention, a Chi Square test will be used to compare frequency of having to reperform biopsies among patients who received the cold saline irrigation compared to patients who did not receive the cold saline irrigation. A level of significance of $\alpha=0.05$ will be used.

- Hypothesis 3: Patients undergoing endobronchial ultrasound and biopsy who receive irrigation with cold saline prior to biopsy will experience a lower incidence of stopping the procedure without biopsy results compared to patients undergoing endobronchial ultrasound and biopsy who do not receive irrigation with cold saline prior to biopsy.

To compare the effects of the intervention, a Chi Square test will be used to compare frequency of stopping the procedure without biopsy results among patients who received the cold saline irrigation compared to patients who did not receive the cold saline irrigation. A level of significance of $\alpha=0.05$ will be used.

- Hypothesis 4: Patients undergoing endobronchial ultrasound and biopsy who receive irrigation with cold saline prior to biopsy will experience a lower incidence of requiring epinephrine to control bleeding after the biopsy compared to patients undergoing endobronchial ultrasound and biopsy who do not receive irrigation with cold saline prior to biopsy.

To compare the effects of the intervention, a Chi Square test will be used to compare frequency of epinephrine administration to control bleeding after the biopsy among patients who received the cold saline irrigation compared to patients who did not receive the cold saline irrigation. A level of significance of $\alpha=0.05$ will be used.

Interim data analysis will occur (1) once approximately 1/3 of the participants have been enrolled in each group and (2) once approximately 2/3 of the participants have been enrolled in each group. If interim calculations at time (1) or time (2) note a significant difference in outcomes between groups, data collection will be completed at that time and final analysis will be completed.

Ethical Considerations

- **Informed consent**

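### The operator is recorded but used in no analysis, so any variation between operators stays in the error term; the tests remain valid, and the cost is precision

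*Combined protocol and SAP*

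**What the plan says.** Under Participants (Sample Size Determination), the protocol states that "44 patients would be needed in each group, for a total sample size of 88 patients", and to allow for missing data "we plan to enroll 120 patients (60 in each group". Under Data Collection, allocation is described as follows: "These envelopes will be filled using a computerized simple random number generator (1:1 randomization) prior to the start of the study". No blocks, strata or other restriction are mentioned.

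The form items in the same section include "Name of MD performing biopsy". The section on the intervention says that pulmonologists, in the plural, perform the procedure in both arms. It also keeps personal information out of the electronic database and does not say whether the operator is entered there, even as a code.

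The Statistical Analysis section gives one test for each hypothesis. For Hypothesis 1, "a Chi Square test will be used to compare frequency of unreadable biopsy slides among patients who received the cold saline irrigation" against those who did not receive it; Hypotheses 2 to 4 follow the same pattern. No stratified test, adjusted model or operator sensitivity analysis appears.

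**The concern.** The operator is the one identified source of variation that is collected for every patient and then left unused. If operators differ in how often slides are unreadable, biopsies are repeated or epinephrine is needed, two things follow from an unadjusted test.

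- The between-operator variation counts as noise, which lowers power.
- Simple randomisation can give one arm more of a particular operator's patients, and nothing in the analysis corrects the realised estimate for that.

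At stake are some power and the credibility of a single realised result, in a small open trial where readers will ask who did the biopsies. Adjusting would use a field that is already on the form.

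**Working it through.** **The plan's own sample size.** Inputs from Sample Size Determination: effect size 0.3 (metric not named), "power of 0.8, and level of significance 0.05". Read as Cohen's w for a two-sided 1-df chi-square test:

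N = (1.960 + 0.842)² / 0.3² = 87.2, rounded up to 88, or 44 per group.

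Noncentral chi-square power at N = 88 is 0.804, so the stated figure reproduces. Read as Cohen's d or h, 0.3 would need about 175 per group.

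**Group sizes (secondary).** Under simple 1:1 randomisation of 120 patients, one arm's size is Binomial(120, 0.5):

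- SD = √120 / 2 = 5.5; 95% range 49 to 71; P(exactly 60/60) = 7.3%.
- P(an arm enrols fewer than 44) = 0.24%.
- Effective N at 49/71 = 4 × 49 × 71 / 120 = 116.0. Power at w = 0.3 is 0.898, against 0.908 at 60/60, a loss of under 1 point. Averaged over all splits it is 0.905.
- If only 88 are analysed, the average is 0.799 against 0.804 at 44/44. The edge of the 95% range (35/53) gives 0.787.

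**Chance operator imbalance.** The number of operators and their volumes are not in the documents. Assuming 2 to 8 operators of equal volume, the simulated probability that some operator's share of patients differs between arms by 10 points or more is 31% to 60%; by 15 points or more, 10% to 21%.

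**Power with and without adjustment.** All of the following is assumed: 4 operators with 30 patients each, N = 120, a 25-point reduction for every operator, simple randomisation and 40,000 simulated trials per row. The tests are the plain chi-square and the Cochran-Mantel-Haenszel (CMH) statistic

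z = Σ(aⱼ − n₁ⱼyⱼ/mⱼ) / √Σ[n₁ⱼn₀ⱼyⱼ(mⱼ − yⱼ) / (mⱼ²(mⱼ − 1))],

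where, for operator j, aⱼ is the events in the saline arm, n₁ⱼ and n₀ⱼ the arm sizes, yⱼ all events and mⱼ all patients. The share of variance due to operator is the variance of the four control risks divided by p̄(1 − p̄): 0.00625/0.25 = 2.5%, 0.02245/0.25 = 9.0% and 0.05125/0.2475 = 20.7% for the last three rows.

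| Control risks by operator (%) | Variance share | Chi-square | CMH | Change (points) | Shift in risk difference from imbalance, 95th percentile (points) |
|---|---|---|---|---|---|
| 50, 50, 50, 50 | 0% | 0.818 | 0.805 | -1.3 | 0 |
| 40, 45, 55, 60 | 2.5% | 0.817 | 0.816 | about 0 | 2.9 |
| 30, 43, 57, 70 | 9.0% | 0.818 | 0.848 | +3.0 | 5.4 |
| 30, 35, 75, 80 | 20.7% | 0.799 | 0.883 | +8.4 | 8.2 |

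Monte Carlo error on each power is about √(0.82 × 0.18 / 40,000) = 0.002. The risks average 50% in the first three rows and 55% in the last. A second simulation of the same comparison, also with 4 assumed operators, gave CMH against chi-square power of 0.804 v 0.818, 0.814 v 0.814, 0.845 v 0.818 and 0.882 v 0.801.

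**Validity.** With no treatment effect, the unadjusted test rejected in 5.2% to 5.3% of simulated trials and CMH in 4.9% to 5.1%. The mean shift from operator imbalance was 0 in every row.

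**The case against.** The strongest objection is that nothing is broken. After simple randomisation the unadjusted test holds its level, and operator imbalance is chance, not bias. No passage states that operators differ, and the gain depends on assumed spreads: it is nil for risks of 40-60%, and slightly negative if operators do not differ. All of this stands, and it makes the point a matter of efficiency. It does not remove the point, because the factor is already recorded, the possible loss is about 1 point, and the possible gain under a wide spread is several times larger.

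Three stronger readings are tempting, and the documents do not support them.

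- A reader might infer that simple randomisation defeats the planned 60 per group. It only fails to guarantee that figure. Envelopes prepared in advance could hold a shuffled 60 and 60, though the text describes no such step, and the power cost is negligible either way.
- A reader might infer that the arms could be badly lopsided at the first look, by taking it to fall after 40 patients in total. The plan sets it "once approximately 1/3 of the participants have been enrolled in each group", so, read literally, the look waits for the smaller arm.
- A reader might conclude that permuted blocks are needed. Unstratified blocks would not balance operators, the gain from equal sizes is tiny, and in an open trial unpredictability is a fair reason for keeping simple randomisation.

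**Conclusion.** The point holds as a minor, inexpensive improvement. The plan collects the operator and ignores it, and so gives up whatever precision operator differences would return. Under the stated assumptions the change in power from adjustment runs from about -1 to about +8 points. No single value, and no equivalent number of patients saved, can be fixed from the documents.

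The result assumes 4 equal-volume operators, a control risk near 50%, the same absolute reduction for every operator, and all 120 patients analysed. It was not worked out for rarer outcomes, which Hypotheses 3 and 4 may be. It also assumes that the operator is settled before the envelope is opened, which the documents do not state.

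The unadjusted tests should not be described as biased or invalid. The group-size matter is one of wording only.

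**What to change.** Before any outcome data are seen:

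1. For the patient-level outcomes, replace the plain chi-square with a Cochran-Mantel-Haenszel test stratified by operator. Write down in advance how low-volume operators are pooled. For Hypothesis 1 this applies if the outcome is defined per patient.
2. Enter a coded operator identifier in the database, with the key kept outside it, so that the rule against personal information is respected.
3. In the sample size paragraph, say approximately 60 per group, or state the step that produces exactly 60 and 60.

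The cost is a few lines of text, one extra coded field and about 1 power point if operators turn out not to differ. Nothing new is collected from patients, and the change works with envelopes that are already filled. If outcome data have already been seen, the adjusted test should be reported as a sensitivity analysis and labelled as added later.

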- Hypothesis 4: Patients undergoing endobronchial ultrasound and biopsy who receive irrigation with cold saline prior to biopsy will experience a lower incidence of requiring epinephrine to control bleeding after the biopsy compared to patients undergoing

endobronchial ultrasound and biopsy who do not receive irrigation with cold saline prior to biopsy.

Background

Endobronchial ultrasounds are used to investigate lymph nodes and/or lesions within or next to the patient's lungs that are visible on ultrasound. The procedure can be used in the diagnosis or staging of cancer. Fine needle biopsies can be obtained through the endobronchial ultrasound scope, and the tissue obtained is immediately placed on cytology slides and promptly taken outside the room to the mobile cytology cart to be stained. The pathologist will then read the prepared slides in real time, offering feedback as to what cells are seen. However, red blood cells often contaminate the sample, due to bleeding from the biopsy site, and thus potentially cover up and block the obtained specimen. This causes more biopsies to be taken and prolongs the procedure and anesthesia time. During normal bronchoscopies, cold saline is used, and has been studied, to decrease bleeding in the airways. This study evaluates the use of cold saline irrigation BEFORE biopsies are taken to potentially decrease the risk of bleeding. Irrigating with cold saline preventatively BEFORE biopsies are taken is not common practice. Additionally,, there has been no research conducted investigating the use of cold saline prior to bronchial biopsies being taken to decrease bleeding. This study seeks to fill this gap in the literature.

Research Plan

- **Study Design**

This study will use a randomized, non-blinded, controlled design with two arms:

- Arm 1: Patient will receive irrigation with 120mL of cold saline 33-39 degrees Fahrenheit), delivered in two 60mL syringes, prior to biopsy
- Arm 2: Patient will receive standard care which involves biopsy without prior irrigation with cold saline.

- **Setting for the study**

The study will take place on Bethesda North Hospital's Endoscopy Department. This unit provides care to approximately 2-12 patients undergoing an endobronchial ultrasound and biopsy per week.

- **Participants**

The study will enroll 120 patients who meet the following inclusion/exclusion criteria:

Inclusion Criteria:

- Undergoing an endobronchial ultrasound and biopsy at Bethesda North Hospital

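### Harms other than bleeding that needs epinephrine are unlikely to be captured equally in the two arms, because the only stated nurse-to-team safety trigger is tied to cold saline and the listed form items include no adverse event item

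*Combined protocol and SAP*

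**What the plan says.** Study Design: "This study will use a randomized, non-blinded, controlled design with two arms". The form that the nurse completes records "Whether patient was assigned to the cold saline group or the standard care group", so the person noting events knows the allocation.

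Data Collection, on safety: "RNs are instructed to call a member of the study team immediately if there are any safety concerns related to the cold saline". A call of this kind stops new enrolment until the study team has reviewed the incident with the pulmonologist involved. The same paragraph adds: "Any adverse events and serious adverse events will be reported to the IRB in compliance with IRB safety policies". It also says that the team will consult the medical team about adverse events. Neither of these two statements is limited to one arm or to a suspected cause.

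Data Collection, on the form: "The form will collect the following information", followed by an itemised list. The list covers allocation, demographics, saline details, biopsy technique, slide counts, repeat biopsy, stopping without a successful reading, procedure times, and "Whether patient needed epinephrine post-biopsy to stop bleeding". It has no general item for adverse events or complications, and none for coughing.

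Intervention section: "Cold saline irrigation is part of the normal procedure and may cause coughing". For the control arm: "Patients randomized to Arm 2 will receive standard care that includes no irrigation with cold saline prior to the biopsy".

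Statistical Analysis: four chi-square tests, on unreadable slides, repeat biopsy, stopping without results, and epinephrine use. No table or comparison of adverse events is planned.

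**The concern.** The nurse's call depends on two things: exposure to cold saline and the nurse's view that saline is the cause. A control patient can seldom meet the first condition. A patient in the saline arm meets the second only if the nurse blames the saline. An event that looks ordinary for the procedure, such as coughing or desaturation, may go unreported in either arm, even if irrigation makes it more frequent.

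IRB reporting of any adverse event is broader on paper. But the protocol does not say how events are to be found, defined, timed or written down, and the listed form items give them no place. The study team can report only what reaches it.

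What is at stake is what the trial can say about harm. The protocol's Background says that preventive irrigation is not common practice and has not been studied before, and the results are meant for publication. A reader will ask whether irrigation caused more problems than biopsy alone. Events not recorded at the visit may not be recoverable at analysis.

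**Working it through.** **Plan's own figure.** The documents give no safety figure. The only related number is the sample size of 88, which reproduces as a two-sided chi-square test with 1 df and effect size w = 0.3: (1.960 + 0.842)² / 0.3² = 87.2, rounded up to 88, or 44 per group. It has no bearing on this point. The planned enrolment of 60 per group is used below.

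**Routes by which a harm could be recorded, by arm:**

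| Route | Saline arm | Control arm | Recorded as data? |
|---|---|---|---|
| Nurse's call to study team | Yes, if attributed to cold saline | Seldom applies: no saline before biopsy | Not stated |
| IRB report or medical-team consultation | Any adverse event | Any adverse event | No method of finding or recording given |
| Epinephrine item on form | Yes | Yes | Yes, tested under Hypothesis 4 |
| General adverse event or cough item | Not listed | Not listed | No |

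Only epinephrine use is recorded in the same way for every patient. It measures bleeding, which the intervention is meant to reduce, and so does not measure harm from the irrigation itself.

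**Illustration of unequal capture.** The event rates and capture fractions are assumptions; none is in the documents. The true rate p is the same in both arms, with 60 per arm. Expected recorded events are 60 × p × capture, with 80% capture in the saline arm throughout. The last column is the chance that an uncorrected chi-square test at a nominal 0.05 would reject, if someone compared the recorded counts.

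| True rate | Control capture | Expected events, saline vs control | Apparent difference | Chance of false rejection |
|---|---|---|---|---|
| 5% | 40% | 2.4 vs 1.2 | 2 points | 0.07 |
| 5% | 20% | 2.4 vs 0.6 | 3 points | 0.12 |
| 5% | 0% | 2.4 vs 0 | 4 points | 0.22 |
| 10% | 40% | 4.8 vs 2.4 | 4 points | 0.14 |
| 10% | 20% | 4.8 vs 1.2 | 6 points | 0.31 |
| 10% | 0% | 4.8 vs 0 | 8 points | 0.72 |
| 20% | 40% | 9.6 vs 4.8 | 8 points | 0.27 |
| 20% | 20% | 9.6 vs 2.4 | 12 points | 0.62 |
| 20% | 0% | 9.6 vs 0 | 16 points | 0.99 |

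Worked row: 60 × 0.10 × 0.80 = 4.8 and 60 × 0.10 × 0.20 = 1.2; 4.8/60 − 1.2/60 = 8% − 2% = 6 points. With 80% capture in both arms the false rejection rate is 0.043 to 0.050 over the same true rates.

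**What full capture could show.** With no events in n patients, the upper limit of the two-sided 95% exact interval is 1 − 0.025^(1/n). For n = 60 this is 6.0%. The plan allows stopping at about one third of enrolment, or 60/3 = 20 per arm, where it is 16.8%. Equal capture would remove the artefact, but the intervals would remain wide.

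**The case against.** The strongest case is that the call is a safety brake on the one added procedure, and was never meant as a data-capture rule. Tying it to cold saline is intelligible. The promise to report any adverse event to the IRB covers both arms whatever the cause, so what is missing is detail on how to do it. All four hypotheses concern efficacy, and no harm comparison is planned that could be biased. The form itself and the IRB policies are not in the documents, and the form carries at least one instruction beyond the itemised list, so the absence of an event item is inferred from that list.

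Most of this stands, and it limits the point. A reader might infer any of the following, none of which the documents support:

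- *The form has no event item at all.* Epinephrine use is recorded in both arms and tested.
- *The plan collects harms from one arm only.* IRB reporting and medical-team consultation are not restricted by arm.
- *A planned result is biased.* The analysis section contains no safety comparison.
- *The bias could equally favour saline.* If control capture is close to zero, under-attribution in the saline arm cannot readily make saline look better than control.
- *The call should be widened to any concern in either arm.* A call stops enrolment, so that would change how often the trial pauses. Symmetric form items meet the concern without it.

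What the objection does not remove is the gap itself. A duty to report events, with no stated way of finding or recording them, does not give a count by arm. The one effect that the protocol itself predicts is missing from a list that is otherwise quite detailed.

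**Conclusion.** The point holds as a gap in symmetric capture. Harms other than bleeding that needs epinephrine are unlikely to be captured equally in the two arms, and cannot be fairly tabulated by arm. The four planned efficacy tests are unaffected.

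The size cannot be derived from the documents. Under the assumed rates and capture fractions above, the artefact runs from 2 to 16 percentage points against saline. That range shows what unequal capture could do, and is not an estimate of what it will do. The conclusion rests on three assumptions: that the itemised list is the full content of the form, that no other document supplies a procedure for finding events, and that nurses follow the call instruction as written. If the actual form already has an event item for both arms, the point reduces to adding a table. It is a cheap improvement: it changes what the trial can report about harm, and nothing in the efficacy analysis depends on it.

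**What to change.** Add the same two or three yes/no items to the existing form for every patient in both arms:

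- any adverse event;
- any serious adverse event;
- coughing that interrupted the procedure.

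State one observation window, the same for both arms, and do not ask the nurse for the cause. In Statistical Analysis, add a descriptive table by randomised arm with risk differences and exact 95% confidence intervals. Leave the call trigger and the pause-and-review rule unchanged.

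The cost is slightly more form completion, one extra table and a few lines of protocol text, with no added staff or visits. Two limits remain. The nurse is still unblinded, so fixed items for everyone reduce uneven recording but do not abolish it. The intervals will also be wide, so the table can describe harms but cannot establish that irrigation is as safe as standard care.

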RESEARCH PROTOCOL

Date	7/31/2023
Title	Evaluating the use of preventive cold saline to decrease bleeding associated with endobronchial biopsy
Principal Investigator	[name], BSN, RN
Sub-Investigators	[name], BSN, RN, CGRN
Research Specialist	[name], RN, CRN-BC
Department	Bethesda North Hospital, Endoscopy Department
Hatton #	23-037

Purpose of Study

Patients undergoing an endobronchial ultrasound and biopsy can experience bleeding during the biopsy. These biopsies are read in real time by pathologists who travel to the endoscopy unit during the procedure. Often, when this happens, the blood contaminates the pathology slides making the slide unreadable. This then requires more biopsies to be performed, thus prolonging the procedure, and increasing anesthesia time. One innovative way to reduce bleeding may be to irrigate the bronchial wall with cold saline, where the biopsy is to be taken, immediately before biopsy, thus causing vasoconstriction and possibly resulting in less blood contamination on the biopsy slides. The current study will evaluate this prophylactic irrigation with saline to control bleeding, thus resulting in a quicker diagnostic result of the biopsies.

Hypothesis or Research Question

- Hypothesis 1: Patients undergoing endobronchial ultrasound and biopsy who receive irrigation with cold saline prior to biopsy will experience a lower incidence of unreadable biopsy slides compared to patients undergoing endobronchial ultrasound and biopsy who do not receive irrigation with cold saline prior to biopsy.
- Hypothesis 2: Patients undergoing endobronchial ultrasound and biopsy who receive irrigation with cold saline prior to biopsy will experience a lower incidence of having to reperform biopsies in order to obtain readable slides compared to patients undergoing endobronchial ultrasound and biopsy who do not receive irrigation with cold saline prior to biopsy.
- Hypothesis 3: Patients undergoing endobronchial ultrasound and biopsy who receive irrigation with cold saline prior to biopsy will experience a lower incidence of stopping the procedure without biopsy results compared to patients undergoing endobronchial ultrasound and biopsy who do not receive irrigation with cold saline prior to biopsy.

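### Four co-equal tests at 0.05, no primary outcome and an undefined interim trigger: on the natural reading, one or more false significant results arise in about 19% to 36% of null trials (about 9.5% to 19% toward benefit)

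*Combined protocol and SAP*

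**What the plan says.** All references are to the combined protocol and SAP.

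- **Hypothesis or Research Question** lists four hypotheses: unreadable slides (H1), repeat biopsy (H2), procedure stopped without results (H3) and epinephrine use (H4). Each is worded as a benefit of cold saline; H1, for example, says that treated patients "will experience a lower incidence of unreadable biopsy slides compared to patients" in standard care. None is labelled primary or secondary.
- **Statistical Analysis** repeats the four under "The following analyses will be performed to address each hypothesis". For H1, "a Chi Square test will be used to compare frequency of unreadable biopsy slides among patients who received the cold saline irrigation", and H2 to H4 follow the same pattern. Each ends with the statement "A level of significance of $\alpha=0.05$ will be used". No ordering, split of alpha or adjustment appears anywhere.
- **Sample Size Determination**: "A power analysis was conducted using a small to medium effect size (0.3), power of 0.8, and level of significance 0.05". This gives 44 per group, raised to 60 per group to cover missing data. It does not say which hypothesis the calculation serves.
- **Statistical Analysis, last paragraph**: "Interim data analysis will occur (1) once approximately 1/3 of the participants have been enrolled in each group", with a second look at about two thirds. If either look should "note a significant difference in outcomes between groups, data collection will be completed at that time and final analysis will be completed". The paragraph does not say which outcome must differ, how many must differ, or what interim significance level applies.

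**The concern.** With four tests of equal standing, each at 0.05, the chance that at least one is falsely significant exceeds 5%. Three looks at accumulating data raise it further. Because the interim trigger is undefined, the study team would be deciding after seeing data which outcome counts and whether enrolment ends. A chance difference in one outcome at about 20 patients per group could close the trial, leaving H1, which matches the stated purpose of the study, with a third of its planned data. Once the data have been seen, a choice of principal outcome is no longer credible and no later analysis repairs it.

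**Working it through.** **Inputs from the plan.** Four chi-square tests (1 df), alpha 0.05 each; effect size 0.3, power 0.80; 44 per group needed, 60 per group planned; 1:1 allocation; looks at about 1/3, 2/3 and the end, so about 20, 40 and 60 per group.

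**Assumed, because the plan is silent.** Correlation between outcomes (0 to 0.9), null event rates, one yes/no result per patient for each outcome, and an uncorrected chi-square unless stated.

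**1. The plan's own figure.** Reading 0.3 as Cohen's w, N = (z(0.975) + z(0.80))² / w² = (1.960 + 0.842)² / 0.09 = 87.2, so 44 per group and 88 in total. The figure reproduces, with power of 80.4% at 88. It is right for one two-sided test and makes no allowance for four tests or three looks.

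**2. Four outcomes, one final look.** With independent outcomes, 1 − 0.95⁴ = 0.185. Toward benefit only, 1 − 0.975⁴ = 0.096. By simulation, the either-direction rate is 15.6% at correlation 0.5 and 9.4% at 0.9.

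**3. One outcome, three looks at |z| > 1.96.** By simulation, 10.7% in either direction and 5.3% toward benefit.

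**4. Four outcomes, three looks, stopping when any one is significant.** Simulation of 500,000 null trials with equicorrelated z-statistics at information 1/3, 2/3 and 1:

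| Correlation | Either direction | Toward benefit | Stops at an interim |
|---|---|---|---|
| 0 | 36.5% | 18.9% | 29.4% |
| 0.3 | 34.5% | 17.3% | 27.7% |
| 0.5 | 31.0% | 15.4% | 24.8% |
| 0.7 | 26.1% | 13.1% | 20.8% |
| 0.9 | 19.1% | 9.6% | 15.1% |

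The comparators for a single test at a single look are 5% in either direction and 2.5% toward benefit.

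**5. Other reading of the trigger.** If all four outcomes had to be significant before stopping, the either-direction rate is 18.6% (independent) to 10.8% (correlation 0.9), and toward benefit 9.6% to 5.4%.

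**6. Check on binary data.** At 20, 40 and 60 per group, with assumed null rates of 50%, 50%, 10% and 5%, independent outcomes and stopping on any, the rates are about 35% either direction and 18% toward benefit. With a continuity correction they fall to about 16% and 8%.

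**7. Effect of a boundary on H1 alone.** O'Brien-Fleming limits z = 3.471, 2.454 and 2.004 give 5.0% overall in either direction and 2.5% toward benefit. Approximate power at the final limit is Φ(√(N × 0.09) − 2.004). At N = 88 this is Φ(2.814 − 2.004) = 79%, and at N = 120 it is Φ(3.286 − 2.004) = 90%. The unadjusted values are 80.4% and 90.8%.

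**The case against.** Nothing elsewhere in the document supplies a primary outcome or a multiplicity rule, so the case on the other side is about size and certainty. Most of it stands.

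- **Direction.** A reader might infer a 36% risk of falsely claiming that saline works. That figure counts differences in either direction; the benefit-only rate is about half.
- **Assumptions.** The documents give no event rates or correlations. These four outcomes probably move together, so the independent case is an upper figure. Whether a continuity correction applies is not stated, and it roughly halves the binary-data rates.
- **Trigger.** A reader might infer that the plan lets any one of the four outcomes end the trial. That is the natural reading, but the sentence is ambiguous; what the text supports is that the trigger is undefined.
- **Rare outcomes.** A reader might picture a chance excess of epinephrine use stopping the trial early. At an assumed 5% rate and 20 per group, significance typically needs 0 against 4 events, with probability about 1.2% at the first look. Commoner outcomes are the likelier early triggers.
- **Intent.** No passage says that success on any one hypothesis would establish efficacy. How a single positive result would be reported is a prediction.
- **Source.** Part of the excess comes from the looks. Naming a primary outcome without an interim boundary would leave 10.7%.

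None of this brings the plan to its nominal level. Even the mildest case for z-statistics, correlation 0.9 with all four outcomes needed to stop, gives 10.8% in either direction.

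**Conclusion.** The concern holds: this is a rule that inflates error if followed as written, and more than missing detail. On the natural reading (any outcome at 0.05, three looks, uncorrected chi-square), the either-direction rate is about four to seven times 5% over correlations from 0.9 to 0. The benefit-direction rate is about four to seven and a half times 2.5%. The absence of a primary outcome and of any error control is certain from the text; the exact size is not, since it depends on the assumed correlations and event rates, the reading of the trigger and the choice of continuity correction. The stated sample size is correct for a single test and is not itself in error.

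**What to change.** 1. Name H1 as the single primary outcome and state that the 44-per-group calculation refers to it.
2. Let only H1 trigger early stopping, against a stated group-sequential boundary. One example is O'Brien-Fleming, z = 3.471, 2.454 and 2.004 at 1/3, 2/3 and the end.
3. Test H2, then H3, then H4 in fixed order, each only if the one before is significant, or use Holm across the three. Do either only if H1 is significant; otherwise treat them as descriptive. State the level that applies to them if H1 stops the trial early.
4. Report all four with 95% confidence intervals in any case, and state whether the chi-square is continuity-corrected.

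**Cost.** Protocol wording and no extra patients. Power for H1 falls by about one percentage point, to about 79% at 88 patients and 90% at 120. H2 to H4 cannot be claimed as confirmed if H1 fails. For comparison, keeping all four co-equal under Bonferroni (0.0125 each, final analysis only) would need about 124 patients for 80% power at w = 0.3, and gives 62% at 88 and 78% at 120.
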